6.11.5 Physical Examination

All physical examination data will be listed, including any clinically significant findings.

6.11.6 C-SSRS

All C-SSRS data will be listed.

6.11.7 Skin Tolerability Assessments

Skin tolerability assessments will be summarized descriptively by treatment using the Skin Irritation Population for each post removal assessment time point as follows:

- The frequency distribution of Dermal Response and Other Effects scores (number, % by category) will be summarized by post removal time point (0.5, 24, 48, and 72 hours post removal)
- The frequency distribution (number, % by score category) of the combined skin irritation score will be summarized by post removal time point (0.5, 24, 48, and 72 hours post removal). The combined skin irritation score at a given time point can range from 0 to 10 and is calculated as the sum of:
 - Dermal Response score which ranges from 0 (none or no evidence of irritation) to 7 (strong reaction spreading beyond the application site
 - Other Effects scores which ranges from 0 (slightly glazed appearance) to 3 (glazing with fissures, film of dried serous exudate covering all or part of the TDS site, or small petechial erosions and/or scabs)
- Number (%) of subjects with a combined irritation score of ≥3 at 30 minutes after TDS removal
- Number (%) of subjects with one or more combined skin irritations scores of ≥3 at any time point between 30 minutes and 72 hours after TDS removal)
- Number (%) of TDS that were removed due to an unacceptable degree of skin irritation

All skin tolerability assessment data will be listed.

6.11.8 Skin Photography

All skin photography data collected in the CRF will be listed, including the assessment date/time and any recorded comments.

6.12 Adhesion Assessments

Page 37 of 61 Confidential

TDS observed adhesion score results (i.e., observed percent adhesion with 0% adhesion assigned to all remaining time points during the wear period in the event of complete detachment) for each TDS will be summarized by treatment as follows using the Adhesion Population:

- Summary statistics (mean, SD, minimum, Q1, median, Q3, maximum) for the mean adhesion score, where the mean adhesion score for each patch is the average of the patch adhesion scores across the entire wear period.
- Adhesion score distribution at each adhesion measurement time point post patch application (i.e., 12, 24, ..., and 168 hours).
- Average adhesion score at each adhesion measurement time point post patch application.
- Number (%) of patches that are completely detached during the 7-day wear period.
- Number (%) of patches with adhesion <50% at any adhesion measurement time point during the 7-day wear period.
- Summary of time a patch was first observed with adhesion <50% during the 7-day wear period.
- Number (%) of patches with adhesion ≥75% at all adhesion assessment time points during the 7-day wear period

In addition to the observed adhesion score, a modified adhesion score will be calculated as follows: the lowest observed adhesion score at each time point after the baseline time point (t_0) will be carried forward to subsequent time points until a lower score is observed. The modified adhesion score results for each TDS will be summarized as follows for the Adhesion Population:

- Summary statistics (mean, SD, minimum, Q1, median, Q3, maximum) for the mean adhesion score computed based on the modified adhesion scores.
- Adhesion score distribution at each adhesion measurement time point post patch application.
- Average modified adhesion score at each adhesion measurement time point post patch application.

All adhesion assessment data (observed adhesion scores as well as the modified adhesion scores as described previously) will be listed.

Within each treatment, to assess whether at least 80% of the TDS applied are at least 75% adhered throughout the 7-day wear period, a one-sided 95% confidence interval (CI) will be determined for the probability (p) that a randomly selected TDS maintains at least 75% adhesion throughout the entire wear period. If the 95% lower confidence limit exceeds 80%, then it will be concluded that at least 80% of patches are at least 75% adhered throughout the wear period.

Page 38 of 61 Confidential

The 95% lower confidence limit will be determined using the Jeffreys prior method. The Jeffreys interval has a Bayesian derivation, and has good frequentist properties (Brown, Cai, Dasgupta 2001; Cai 2005). It is obtained using the non-informative Jeffreys prior for the binomial proportion p, namely a Beta distribution with parameters ($\frac{1}{2}$, $\frac{1}{2}$). It is a conjugate prior with a posterior distribution for p that is Beta (X+ $\frac{1}{2}$, n-X+ $\frac{1}{2}$), where n is the number of TDS in the Adhesion Population for the treatment and X is the number of TDS with at least 75% adhesion throughout the wear period. The 95% lower confidence limit (CL) will be formed as follows:

CL = Beta(0.05; $X + \frac{1}{2}$, $n - X + \frac{1}{2}$)

where in the event that x=0, the lower limit is defined to be 0.

The Jeffreys one-sided CI has been recommended by Cai (2005). It is one of the few CI methods with the advantage of being equal-tailed (i.e., the probabilities of the interval lying above or below the true value are equal). The Wilson score interval, for example, has good coverage probabilities as a method for constructing two-sided confidence intervals for p, but has a systematic bias in that it is centered too close to p=0.5 making it unsuitable for construction of a one-sided interval. Similarly, the one-sided Wald interval and the likelihood ratio interval (formed by inversion of the likelihood ratio test) also have pronounced systematic bias (Cai 2005; Newcombe 1998).

Adhesion results from 3 previous studies are available (Table 1). In Study P-15086 (Periods 2 and 3 where the incidence of patch taping and smoothing was extremely low), point estimates of the probability that a randomly selected TDS remains at least 75% adhered during the 7-day wear period were 0.94 (32/34) for the 5 mg/day TDS and .96 (126/135) for the 10 mg/day TDS. In study P-16010, estimates that patches were at least 80% adhered throughout the 7-day wear period were 0.94 (80/85) and 0.91 (307/338) for the 5 mg/day and 10 mg/day TDS, respectively. The estimate (at least 80% adhered throughout the wear period) for the 10 mg/day TDS applied to the back in Study P=15086 was 0.85 (51/60).

Subjects received 5 mg/day TDS during Week 1 and a 10 mg/day TDS weekly during Weeks 2-5 in studies P-15086 and P-16010. Adhesion results show some indication of clustering within subject in Study P-16010 but not in Study P-15086. Individual subjects that had adhesion <75% (<80% in Study P-16010) during the TDS wear period are listed by week in Table 2. In Study P-15086, 5 TDS (10 mg/day) from 5 different subjects had 10 mg/day patches that were <75%

Page 39 of 61 Confidential

adhered at some point during the wear period. In contrast, there were 31 TDS (10 mg/day) from 19 subjects that were <80% adhered during the wear period in Study P-16010.

	P-15086 (Peri	ods 2 and 3)				
TDS	[1]]	Study P-1	6010 [2]	Study P-1	6012 [2]
Application	Adhered	.^	Adhered	.^	Adhered	.^
Week	>75%	$p_{0.75}$	>80%	$p_{0.80}$	>80%	$p_{0.80}$
Week 1	32/34	0.94	80/85	0.94	51/60	0.85
Week 2	33/34	0.97	76/85	0.89		
Week 3	31/33	0.94	75/85	0.88		
Week 4	31/32	0.97	78/85	0.92		
Week 5	31/32	0.97	78/83	0.94		
Weeks 2-5	126/131	0.96	307/338	0.91		

Table 1. Adhesion Results from Studies P-15086, P-16010, and P-16012

[1] In Study P-15086, whole-patch adhesion was measured every 12 hours on a 5-point scale (0=100% adhered; 5=0% adhered). A score <2 at all assessment time points indicated that a patch was >75% adhered throughout the wear period. Subjects had 5 mg/day patches (50 cm² active drug area) applied during Week 1 and 10 mg/day patches (105 cm² active drug area) applied weekly during Weeks 2-5.

[2] In Studies P-16010 and P-16012, whole-patch adhesion was measured every 12 hours on an 11-point scale (0=100% adhered; 11=0% adhered). A score <3 at all assessment time points indicated that a patch was >80% adhered throughout the wear period. In study P-16010, subjects had 5 mg/day patches (53.5 cm² active drug area) applied during Week 1 and 10 mg/day patches (107 cm² active drug area) applied weekly during Weeks 2-5. In Study P-16012, patches applied to the back (10 mg/day patches; 107 cm² active drug area) during a one-week treatment period are included.

Source: Table 14.3.9.3.1 (Study P-15086); Table 14.3.9.1.1 (Study P-16010); Table 14.3.9.1.1 (Study P-16012)

Study CL-P-20004 will enroll approximately 60 subjects, with around 48 subjects expected to complete the 109-day in-clinic study. Prior single-dose crossover studies conducted by the Sponsor indicate that most dropouts occur during the first one to two treatment periods. As a result, approximately 55 subjects are expected to have TDS included in the Adhesion Population for TDS A (5 mg/day TDS), and approximately 50 subjects are expected to have TDS included in the Adhesion Population for TDS B (10 mg/day TDS). The number of 5 mg/day TDS (TDS A) in the Adhesion Population will be approximately 270, and the number of 10 mg/day TDS (TDS B) in the Adhesion Population will be approximately 245.

Based on the three previous studies (Table 1), the point estimate for p is expected to be 0.90 - 0.95 (i.e., fewer than 13 and 11 TDS are expected to have < 75% adherence at one or more adhesion assessment time points during the wear period for TDS A and TDS B, respectively).

In the range for p that is expected in the current study, the Jeffreys lower confidence limit should provide good coverage probability (Cai 2005; Newcombe 2011).

Page 40 of 61 Confidential

As a sensitivity analysis, the Clopper Pearson method of constructing the 95% lower confidence limit also will be implemented for each treatment. The Jeffreys prior confidence interval can be regarded as a continuity-corrected version of the Clopper–Pearson confidence interval and is always contained within the Clopper-Pearson confidence interval (Brown et al. 2001). This one-sided 95% Clopper-Pearson CI method is very conservative and has coverage probability \geq 95% for all p between 0.0 and 1.0.

As a second sensitivity analysis, a one-sided 95% confidence interval that takes into account clustering of adhesion failures (i.e., TDS with <75% adhered during the wear period) within subject will be presented.

A generalized linear mixed model (GLMM) analysis of the probability that a patch is at least 75% adhered during the entire wear period will be used. The GLMM will model variation at both the individual and patch level. The GLMM will assume that each subject has an underlying, unobservable probability that governs the tendency for a patch to remain at least 75% adhered during the wear period. This probability is assumed to vary from subject to subject.

Let π_i denote the probability that a patch applied to the ith subject will remain at least 75% adhered during the wear period. Let y_{ij} be the response variable for the jth patch applied to the ith subject:

 $y_{ij} = \begin{cases} 1 \text{ if the TDS is at least 75\% adhered throughout the wear period} \\ 0 \text{ if the TDS is less than 75\% at some point during the wear period} \end{cases}$

The number of patches applied to the i^{th} subject with "favorable" adhesion (i.e., $y_{ij} = 1$), has a binomial distribution conditional on the random effect of subject:

 $y_i \mid s_i \sim Binomial(n_i, \pi_i)$

where n_i is the number of patches applied to the i^{th} subject. In the current study, n_i is usually 5 but can range from 1 to 5).

Since the log likelihood function of a binomial random variable with n Bernoulli trials and favorable outcome probability π is linear in the logit, $\log(\pi/(1-\pi))$, a linear model will be fit to the logit.

Using the logit link function, a conditional GLMM for the adhesion analysis is as follows:

$$\eta_i = \log\left[\frac{\pi_i}{(1-\pi_i)}\right] = \eta + s_i$$

Page 41 of 61 Confidential

where η is the intercept and s_i is the effect of the ith subject assumed to be independent, identically distributed N(0, σ_s^2).

Here s_i is a latent variable centered at 0 that quantifies an individual subject's tendency (i.e., probability) for having an applied TDS remain at least 75% adhered during the 7-day wear period in relationship to other subjects. Variation in s_i, σ_s^2 , represents variation in this propensity among subjects.

The inverse link function for this logistic model will be used to estimate π (Stroup et al 2018). From the link function, we have:

$$\hat{\pi} = \frac{1}{(1 + e^{-\hat{\eta}})}$$

with standard error estimate

 $SE[\hat{\pi}] = [\hat{\pi}(1 - \hat{\pi}) * SE(\hat{\eta})]$

and a 90% two-sided confidence interval obtained by applying the inverse of the link function to the upper and lower confidence bounds of the logistic-scale 90% two-sided confidence interval.

Page 42 of 61 Confidential

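### The limits that decide and check the 80% adhesion claim treat up to five patches per subject as independent; if failures cluster as in P-16010, the one-sided error at a true rate of 80% is about 12–14% instead of 5%

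*SAP*

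**What the plan says.** Adhesion of each strength is a secondary objective. SAP 6.12 sets a pass/fail rule per treatment: "If the 95% lower confidence limit exceeds 80%, then it will be concluded that at least 80% of patches are at least 75% adhered". On the method it says: "The 95% lower confidence limit will be determined using the Jeffreys prior method". The limit is the 5th percentile of Beta(X + ½, n − X + ½), "where n is the number of TDS in the Adhesion Population for the treatment", and X counts the patches that stay at least 75% adhered. The same section expects about 270 patches from about 55 subjects (5 mg) and about 245 from about 50 subjects (10 mg), usually five per subject.

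On earlier data the SAP writes: "Adhesion results show some indication of clustering within subject in Study P-16010", and adds that P-15086 showed none. It plans two sensitivity analyses. The first is Clopper-Pearson on the same counts, described thus: "This one-sided 95% Clopper-Pearson CI method is very conservative and has coverage probability" of at least 95% for every p. The second is a generalized linear mixed model (GLMM) with a random subject intercept, meant to allow for clustering. Its interval is presented; the decision rule does not refer to it.

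**The concern.** A binomial limit on n patches has its stated error only if patches fail independently. Five patches on one back share skin, sweating, hair and habits, so failures may well come from the same subjects. If they do, the pooled proportion varies more than n suggests, the lower limit sits too high, and the claim is made too often when the true rate is only 80%. The first check cannot reveal this because it shares the assumption. The analysis that could reveal it has no role in the decision, and nothing says what follows if it disagrees.

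**Working it through.** **Inputs (SAP 6.12).** One-sided 5%; threshold 0.80; n = 270 and 245; five patches per subject, taken as 54 × 5 and 49 × 5 to match those totals. P-16010 (text and Table 1): 31 failures in 338 10 mg patches, 19 subjects affected, weekly denominators 85, 85, 85, 83. I read the last as 83 subjects with four patches and two with three. P-15086: five failing 10 mg patches among 131, from five subjects.

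**Step 1: the plan's own error under independence.** The smallest X whose limit exceeds 0.80 is 227/270 (84.1%) and 207/245 (84.5%) for Jeffreys, and 228/270 and 207/245 for Clopper-Pearson. The binomial tail at p = 0.80 is 5.2% and 4.4% (Jeffreys), and 3.7% and 4.4% (Clopper-Pearson). The nominal 5% reproduces, up to discreteness. For the 10 mg patch the two methods share one pass mark, so at these numbers the check adds no protection.

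**Step 2: clustering in P-16010.** The failure rate is 31/338 = 0.0917. Under independence the expected number of subjects with any failure is 83 × (1 − 0.9083⁴) + 2 × (1 − 0.9083³) ≈ 27.0, against 19 observed. The beta-binomial ICC that gives 19 is 0.30. The SAP text available does not show how the 31 failures divide among the 19 subjects. Over every division that fits the totals, the ANOVA estimate of the ICC runs from 0.19 to 0.47.

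**Step 3: error at true p = 0.80 with clustering.** Exact convolution of beta-binomials, subject by subject:

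| ICC | Jeffreys, 270 | Jeffreys, 245 | Clopper-Pearson, 270 | Clopper-Pearson, 245 |
|---|---|---|---|---|
| 0 | 5.2% | 4.4% | 3.7% | 4.4% |
| 0.1 | 8.5% | 7.4% | 6.6% | 7.4% |
| 0.2 | 11.5% | 10.3% | 9.3% | 10.3% |
| 0.30 | 14.0% | 12.7% | 11.7% | 12.7% |
| 0.47 | 17.5% | 16.3% | 15.1% | 16.3% |

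A logit-normal subject effect matched to P-16010 gives up to 15.9% (Jeffreys, 270).

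**Step 4: where the conclusion would change.** At ICC 0.30 the design effect is 1 + (5 − 1) × 0.30 = 2.2, so effective n is 270/2.2 ≈ 123 and 245/2.2 ≈ 111. Jeffreys lower limits, unadjusted → adjusted (before the small t-adjustment described under the fix):

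| Observed rate | n = 270 | n = 245 |
|---|---|---|
| Pass mark (84.1% / 84.5%) | 0.8015 → 0.7807 | 0.8039 → 0.7821 |
| 86% | 0.8225 → 0.8024 | 0.8205 → 0.7992 |
| 87% | 0.8335 → 0.8138 | 0.8315 → 0.8107 |
| 90% | 0.8668 → 0.8485 | 0.8650 → 0.8456 |

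The claim is at risk only for observed rates of about 84–86%.

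**The case against.** The plan does not overlook dependence. It reports the P-16010 clustering openly and pre-specifies a GLMM to allow for it. A reader might infer that clustering was ignored; the documents do not support that. What stands is narrower: the GLMM is only presented.

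A reader might also infer that the trial's error simply is 12–15%, or two to three times nominal. That goes too far, for these reasons:

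- The ICC is inferred from a few totals in one of two earlier multi-week studies.
- P-15086 points the other way, though weakly: given five failures, all five fall in different subjects about 79% of the time under independence and still about 9–10% of the time at ICC 0.30.
- P-16010 used an 80% cut on an 11-point scale, not 75% on a percentage scale.
- Each subject in those studies wore only one 5 mg patch, so nothing is known about within-subject clustering for that strength.
- The ICC was estimated near p = 0.91 and is applied here at p = 0.80.
- The patch has since changed: Protocol Section 3 describes process changes that include stronger bonding between the active layer and the overlay.
- At ICC 0.1 the Jeffreys error is 7–9%, which is less than double.

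Nor is the Clopper-Pearson sentence shown to be false. It is a correct property of independent binomial trials, and this trial's clustering is not known from the documents. The fair criticism is that the condition is left out.

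Finally, the SAP expects p of 0.90–0.95. At ICC 0.30 the unadjusted rule passes 97–98% of the time at p = 0.90 and nearly always at 0.95, so the outcome would probably be the same. That stands and limits the weight of the point. Lower rates are not hypothetical, however: Table 1 shows 51/60 = 85% for the 10 mg patch on the back in P-16012, at the stricter 80% cut.

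**Conclusion.** The structural point holds. The deciding limit and its first check both have their stated error only if patches on one subject fail independently, and the SAP cites evidence that they may not. At a true rate of 80% the error is about 4–5% with no clustering, 7–9% at ICC 0.1, roughly 10–11% at 0.2, 12–14% at 0.30 (up to about 16% under a logit-normal model) and 15–17.5% at 0.47. These figures rest on an ICC that the documents do not give. They assume a beta-binomial model and carry 10 mg results at an 80% cut over to both strengths at 75%. They describe what the rule permits and do not show that this trial's adhesion conclusion is wrong. The point is worth correcting because adhesion is a formal secondary claim and the correction is cheap. It would matter in practice only for an observed rate of about 84–86%.

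**What to change.** Make the deciding limit cluster-adjusted for the marginal patch probability, the p that the SAP defines for a randomly selected patch. One workable form, with k subjects, mᵢ patches and yᵢ successes in subject i, and p̂ = X/n:

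- variance from subject totals: v = [k/(k − 1)] × Σ(yᵢ − p̂mᵢ)² / n²;
- design effect: DE = v / [p̂(1 − p̂)/n], set to 1 if there are no failures;
- n_eff = n / max(1, DE), multiplied by (z₀.₉₅ / t₀.₉₅ on k − 1 df)²;
- limit = Beta(0.05; p̂·n_eff + ½, (1 − p̂)·n_eff + ½).

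Keep unadjusted Jeffreys and Clopper-Pearson as supportive, and state that the coverage of at least 95% holds only if patches are independent. Promoting the GLMM as written would not do. It back-transforms the intercept, which gives the probability for a subject with a zero random effect. At a marginal rate of 0.80 with clustering like that in P-16010, that probability is about 0.915.

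**Cost.** A paragraph of SAP text and a few lines of code. In simulation the adjusted limit's error was about 4.1–5.7%. Power at p = 0.90 stays above 99% without clustering; at ICC 0.32 it falls from about 97–98% to about 88–91%, still above the 80% in SAP Section 4. The SAP already carries a post-database-lock addendum. If the change comes after lock, label the adjusted limit post hoc, report it beside the pre-specified one, and say how a disagreement is read.

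### The GLMM planned to allow for clustering of adhesion failures estimates a subject-specific probability that lies above the marginal p of the 80% rule, so a GLMM limit above 80% does not show that the Jeffreys conclusion survives clustering

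*SAP*

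**What the plan says.** SAP 6.12 defines the target as the "probability (p) that a randomly selected TDS maintains at least 75% adhesion throughout the entire wear period". The rule follows: "If the 95% lower confidence limit exceeds 80%, then it will be concluded" that adhesion is acceptable. The limit is the 5th percentile of Beta(X + ½, n − X + ½), where "n is the number of TDS in the Adhesion Population for the treatment". It has no subject term. Protocol 17.4 leaves the method and its justification to the SAP.

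Two sensitivity analyses are planned. The first is Clopper-Pearson, which also treats patches as independent; the SAP describes it thus: "one-sided 95% Clopper-Pearson CI method is very conservative and has coverage probability" of at least 95%. The second is a random-intercept logistic GLMM, logit(π_i) = η + s_i with s_i ~ N(0, σ_s²), which the SAP itself calls conditional. Then: "The inverse link function for this logistic model will be used to estimate" π, as 1/(1 + exp(−η̂)). The interval applies the same inverse logit to the limits of η. Addendum 2.5 keeps this intercept estimate, labels it as a population-average proportion, and drops `method=quad` from the code.

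On whether failures cluster, the SAP reports: "Adhesion results show some indication of clustering within subject in Study P-16010 but not in Study P-15086". The counts given are that "there were 31 TDS (10 mg/day) from 19 subjects that were <80% adhered during the wear period in Study P-16010", while in P-15086 "5 TDS (10 mg/day) from 5 different subjects had 10 mg/day patches" below 75%.

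**The concern.** The accept rule averages over patches and therefore over subjects. The GLMM figure does not: it sets s_i to zero and reports the probability for the median subject. No step integrates over s_i. Because the inverse logit is concave above 0.5, the two quantities differ in a known direction when p is high: the GLMM value is larger, and the gap grows with σ_s.

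A clustered limit is there to show how much of the Jeffreys margin is lost when up to five patches come from one back. It should fall when failures cluster. This one is aimed at a larger quantity and can rise, so it may appear to support a Jeffreys pass that a limit for p would not support. No other planned analysis covers clustering, and the population-average label hides the change of target.

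**Working it through.** **Inputs.** From SAP 6.12: about 245 patches at 10 mg/day and 270 at 5 mg/day, usually five per subject; expected p of 0.90–0.95; P-16010 with 307/338 patches adhered in Weeks 2–5 and 31 failures in 19 of 85 subjects. The within-subject correlation (ICC) for this trial is not in the documents. It is an assumption here, shown at 0.1/0.2/0.3.

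**The plan's own figure.** 307/338 = 0.908, which reproduces the SAP's 0.91. Its Jeffreys limit is 0.880. The SAP gives no numerical GLMM result.

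**Is clustering plausible?** The P-16010 denominators imply 83 subjects with four patches and 2 with three. With failure probability 31/338 = 0.0917 and independence, the expected number of subjects with a failure is 83 × (1 − 0.908⁴) + 2 × (1 − 0.908³) ≈ 27. The observed number is 19. P-15086 shows none, but five failures are too few to exclude it. P-16010 used an 80% cut-off, so it does not give the ICC for this trial.

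**What the GLMM targets.** Marginal p = E[1/(1 + exp(−(η + s)))] with s ~ N(0, σ_s²); ICC = Var(π_i)/[p(1 − p)]. Solve for η and σ_s, then compute 1/(1 + exp(−η)).

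| ICC | σ_s at p = 0.80 | GLMM target, p = 0.80 | GLMM target, p = 0.90 |
|---|---|---|---|
| 0 | 0 | 0.80 | 0.90 |
| 0.1 | 0.84 | 0.83 | 0.93 |
| 0.2 | 1.30 | 0.86 | 0.95 |
| 0.3 | 1.76 | 0.89 | 0.97 |

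**How often each limit exceeds 0.80 when true p is exactly 0.80** (49 subjects × 5 patches; nominal 5%).

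| Limit | ICC 0.1 | 0.2 | 0.3 |
|---|---|---|---|
| Jeffreys | 7% | 10% | 13% |
| GLMM intercept, pseudo-likelihood | 7% | 12% | 19–20% |
| GLMM intercept, quadrature | 14% | 32% | 52–55% |
| Quadrature GLMM integrated to marginal p | 5–6% | 4–5% | 5% |
| Cluster-robust logit | 4.5–5% | 4.5–5% | 4.5–5% |

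Replicates per cell: 100,000 for Jeffreys and cluster-robust, about 3,000 for pseudo-likelihood, 1,500 for quadrature. Both GLMM fits are re-implementations outside SAS. The pseudo-likelihood row assumes that this is the default once `method=quad` is dropped.

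**Where the decision is exposed.** Jeffreys passes from 207/245 = 0.845 (limit 0.804) and 227/270 = 0.841; Clopper-Pearson from 207 and 228. A clustered limit on the logit scale, logit(q) − t × √[(1 + 4·ICC)/(n·q(1 − q))] with q = x/n and t on subjects minus 1, passes from 209/211/212 of 245 (0.853/0.861/0.865) and 230/231/233 of 270 (0.852/0.856/0.863). At n = 245, Jeffreys passes while the simulated cluster-robust limit fails in 11/18–19/24% of trials at p = 0.85, 2/5–6/10% at p = 0.90, and at most 0.13% at p = 0.95.

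**On P-16010 counts**, over the possible ways of placing 31 failures in 19 subjects: limits for the marginal p are 0.857–0.870, below Jeffreys' 0.880. The GLMM intercept limit is 0.888–0.897 by pseudo-likelihood (16 of 19 patterns converged) and 0.919–0.950 by quadrature. All exceed 0.80, but only the intercept limit moves up.

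**The case against.** The strongest reply is that nothing is decided on the GLMM. Adhesion is a secondary objective, the accept rule uses Jeffreys alone, and the GLMM is a second sensitivity analysis with no rule for reading it. At the expected 0.90–0.95 a correct clustered limit would rarely disagree with Jeffreys. All of that stands, and it limits the consequence; it does not make the reported quantity the one intended.

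The fitting method matters too. With `method=quad` dropped, the inflation is probably the smaller row of the table, close to Jeffreys' own at ICC 0.1. In a small simulation at that ICC (300 replicates per cell), the pseudo-likelihood limit rose above Jeffreys in only about 6% of runs at p = 0.80 and 37% at p = 0.90; at ICC 0.3 it rose in 85–93%. The printed code is damaged by extraction, so neither method can be confirmed.

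A reader might infer that the GLMM tells us nothing, that the Jeffreys conclusion is unsafe, or that σ_s² will go unreported. The documents do not support these. The error has one direction, so a GLMM limit below 80% is still informative. The margin at the expected p is wide. Only the title of Table 14.3.7.21 is visible, and a title does not show what the table omits.

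**Conclusion.** The point holds as a mismatch of target, readable from the SAP's own equations and independent of how the model is fitted. The GLMM limit is too favourable as a limit for p whenever p > 0.5 and σ_s > 0: a value above 80% is not reassurance about clustering, and a value below 80% remains a warning. The size depends on an assumed ICC and on a fitting method that cannot be confirmed. At true p = 0.80 and ICC 0.1/0.2/0.3, false support runs at about 7/12/19–20% under pseudo-likelihood and 14/32/52–55% under quadrature, against about 5% for a marginal limit. The adhesion decision itself is exposed only for observed proportions of about 0.84–0.865.

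**What to change.** Keep the Jeffreys rule unchanged. In SAP 6.12, replace the back-transformed intercept with a one-sided 95% lower limit for the marginal p that allows for clustering by subject. Either of these would do:

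- fit the existing GLMM by quadrature and integrate the inverse logit over N(0, σ_s²), with a delta-method limit; or
- use an intercept-only GEE, or a pooled logit with cluster-robust standard error and t on subjects minus 1, falling back to the Jeffreys limit if there are no failures.

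If the GLMM is kept, report σ_s² and correct the population-average label in the addendum code. Declare the limit as a sensitivity analysis added after database lock, and attach no new accept gate to it.

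The cost is one further limit on data already collected; the decision rule and its power do not change. The sensitivity limit will be somewhat lower when failures cluster: at p = 0.90, where adhesion truly exceeds 80%, it would not support a correct Jeffreys pass in 2/5–6/10% of trials at ICC 0.1/0.2/0.3 (n = 245). The cluster-robust version is slightly liberal near p = 0.95 with strong clustering: at ICC 0.3 it exceeds the true p in 6.5–7.3% of trials instead of 5%.
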